**Table 3 : Time-window for statistical analysis**

| Visit          | Theoretical time    | Time-window |             |
|----------------|---------------------|-------------|-------------|
|                |                     | Lower limit | Upper limit |
| Administration | D1                  | D1          | D1          |
| EoH            | Between D13 and D18 | D2          | D18         |
| 3 months       | D91                 | D19         | D136        |
| 6 months       | D183                | D137        | D273        |
| 12 months      | D365                | D274        | D456        |
| 18 months      | D548                | D457        | D639        |

Note: time-windows described in section 6.1 of the protocol were defined for operational and monitoring activities. They will not be used for statistical analysis.

Note: Time-windows will be applied and calculated visits will be used for the analysis of the following data:

- Vital signs
- Clinical signs and symptoms of HAT
- Physical examination
- Neurological examination
- HAT diagnosis (i.e. examination of blood, lymph and CSF samples)
- Laboratory examination

Time-windows will not be used for calculation of the primary endpoint and secondary endpoints since it is included in the algorithms presented in Sections 10.1 to 10.3. Time-windows will not be used for calculation of the time to proven and definitive failure endpoint since it is included in the algorithm presented in Section 6.3.

## 7.6. Handling of missing data

### 7.6.1. Handling of missing data for primary and secondary efficacy endpoints

#### Method used for primary analysis:

Handling of missing data is included in the derivation algorithms for outcome at 18, 12 and 6 months (cf. [Section 10](#)).

#### Fair case method (for sensitivity analysis):

The algorithm defined in [Section 10](#) will be used to derive the outcome at 18, 12 and 6 months, with the following changes. Responses of the following patients will be replaced using a **resampling approach**:

- Patients lost to follow-up (prior or at visit 18, 12 and 6 months, respectively)
- Patients who refused all post treatment lumbar punctures
- Patients without WBC in CSF data at the corresponding visit (6, 12 or 18 months, respectively) and no proven success according to prior or posterior visit(s) (see algorithm defined in [Section 10](#) for details)

The resampling will be performed with a **hot deck multiple imputation** method as follows:

- Responses will be replaced by simple random sampling (with replacement) among non-missing responses (=donnors selection)
- The initial seed for random number generation used to select donor units will be set to 495.
- This step will be repeated 100 times in order to produce 100 samples (=number of donor units).
- Each sample will be analyzed as described in section 8.6.1 (i.e. the estimate, its 95% Jeffrey CI and corresponding standard error will be computed for each samples).
- The results of each of these analyses (estimates and standard errors) will be combined using Rubin's rules as implemented in the SAS MIANALYZE procedure to provide combined estimate and the 95% Jeffrey CI.

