#### 4.6. Sample Size Determination

Cf. Section 9.1 of the Protocol:

“The sample size is based on the largest number of patients who can be enrolled within a reasonable timeframe. It is expected that 155 late-stage patients should be enrolled within approximately 2 years. A provision of 5% (7 patients) is planned in order to allow for replacement of patients lost to follow-up who fled the region due to armed conflict or natural disaster. Approximately 50 early- and intermediate-stage patients could be enrolled within this timeframe. As a reminder, enrolment of early- and intermediate-stage patients will begin approximately 6 months after the start of enrolment of late-stage patients and will end at the same time”.

“If the observed success rate is around 89% (the same as the expected rate for fexinidazole and the observed rate with eflornithine) then the width of the 95% Jeffreys confidence interval will be 9.8% (83.4%–93.2%). The width decreases with an increase in the success rate to reach 7.4% (89.7%–97.1%) for a 94% success rate. In contrast, the precision is not highly sensitive to the sample size. With 200 patients, the width of the confidence interval is 8.7% (84.1%–92.8%) for an 89% success rate. Indeed, the sample size must increase by 50%, i.e. 300 patients instead of 200, to reduce the width of the lower arm of the 95% confidence interval by one percentage point”.

“In early- and intermediate-stage patients, the expected success rate is around 91%, i.e. the same as for pentamidine. The width of the confidence interval with 50 patients will be around 17%”.

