### 7.2. Type I error

For all analyses, the type I error ( $\alpha$ ) is set to 0.05, two sided.

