
| Derivation algorithm for stage 1 and intermediate stage (month 18)   | Derivation algorithm for stage 2 (Month 18)  |
|--|--|
| 
Earlier (before M18) unfavorable outcome: increase of WBC in CSF at M6 or M12 with respect to EOH
 
⇒ YES ⇒ 9: Failure (stop)
 
↓
 
NO (no information or no earlier unfavorable assessment)
 
↓
 
Patient has clinical signs or symptoms at M18 evoking a failure
 
⇒ YES ⇒ 10: Failure (stop)
 
↓
 
NO (no clinical signs or symptoms evoking a relapse at M18)
 
↓
 
WBC in CSF ≤ 20 at M12 or absence of LP at M12 and for both cases no increase WBC in CSF at M6 with respect to EOH and no sign and symptoms at M18 evoking a relapse:
 
⇒ YES ⇒ 11: Success (stop) [b]
 
↓
 
NO (at least one criterion not met)
 
↓
 
Patient refused all post treatment lumbar punctures
 
⇒ YES ⇒ 12: Failure (stop) [a,b]
 
↓
 
All other cases ⇒ 13. Failure
 | 
Earlier (before M18) unfavorable outcome: WBC in CSF > 50 at M6 or WBC in CSF > 20 at M12 or increasing between M6 and M12
 
⇒ YES ⇒ 9: Failure (stop)
 
↓
 
NO (no information or no earlier unfavorable assessment)
 
↓
 
Patient has clinical signs or symptoms at M18 evoking a failure
 
⇒ YES ⇒ 10: Failure (stop)
 
↓
 
NO (no clinical signs or symptoms evoking a relapse at M18)
 
↓
 
WBC in CSF ≤ 20 at M12 or in absence of LP at M12 and for both cases WBC in CSF ≤ 50 at M6 and no signs and symptoms at M18 evoking a relapse:
 
⇒ YES ⇒ 11: Success (Stop) [b]
 
↓
 
NO (at least one criterion not met)
 
↓
 
Patient refused all post treatment lumbar punctures
 
⇒ YES ⇒ 12: Failure (Stop) [a,b]
 
↓
 
All other cases ⇒ 13. Failure
 |

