**For sensitivity analyses:**

[a] will be considered as a success with the best case method (see [Section 7.6.1](#)).

[b] re-sampling will be applied with the fair case method (see [Section 7.6.1](#)).

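### The 18-month fair-case analysis has two unreconciled lists of patients to resample: the text of SAP 7.6.1 and the [b] flags in SAP 10.1

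*SAP*

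**What the plan says.** SAP 8.6.1.2 plans sensitivity analysis #4 on stage 2 mITT patients with the fair-case method. Two places say whom that method resamples. Below, the numbered end points of the SAP 10.1 algorithm are called boxes.

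- **SAP 7.6.1, fair case.** Three groups are resampled: patients lost to follow-up; patients who refused all post-treatment punctures; and patients without a CSF white cell count at the visit "and no proven success according to prior or posterior visit(s"), with a reference to Section 10 for details. Replacement values are drawn from the non-missing responses, 100 times.
- **SAP 10.1.** The note under the algorithm says of the flag: "b] re-sampling will be applied with the fair case method", and refers back to 7.6.1. In both columns [b] stands on box 4 (lost to follow-up), box 11 (no usable month-18 count, success taken from earlier visits) and box 12 (refused all punctures). In the stage 2 column, box 11 requires a month-12 count of 20 or less, or "in absence of LP at M12 and for both cases WBC in CSF ≤ 50 at M6", and no signs of relapse at month 18. Box 9 (earlier unfavourable count), box 10 (signs at month 18) and the residual box, "All other cases ⇒ 13. Failure", carry no flag.

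**The concern.** Boxes 4 and 12 match the first two groups in 7.6.1. The remaining boxes do not line up.

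- Box 13 has no usable count at month 18 or later and no success, so it meets the third group, yet it is not flagged.
- Boxes 9 and 10 also meet the third group on its words. They are failures on observed evidence, so redrawing them would hardly be a missing-data exercise.
- Box 11 is flagged, although its success comes from a prior visit, which the third group appears to leave alone.

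A programmer following the flags redraws presumed cures and keeps all unassessed failures. One following the text may do the reverse. The donor pool changes as well. This is the only multiple-imputation check among sensitivity analyses #1 to #6. SAP 12 requires double programming only for the derivation of the primary endpoint, so no planned step is sure to catch a divergence. If the choice is left open, it could be made after outcomes are known in an open-label trial.

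**Working it through.** **Plan's own precision.** SAP 4.6: "It is expected that 155 late-stage patients should be enrolled within approximately 2 years". SAP 7.2: alpha "is set to 0.05, two sided". The Jeffreys interval is given by the 2.5% and 97.5% quantiles of Beta(x+0.5, n−x+0.5).

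- 138/155 (89.0%): 83.40% to 93.23%, width 9.83. SAP 4.6 states "the width of the 95% Jeffreys confidence interval will be 9.8% (83.4%–93.2"%). Reproduced.
- 146/155 (94.2%): 89.67% to 97.09%, width 7.42. SAP 4.6 has the width falling "to reach 7.4% (89.7%–97.1%) for a 94% success rate". Reproduced.

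SE = √(p(1−p)/155): 2.51 points at 138/155 and 1.88 points at 146/155.

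**Expected fair-case rate.** Let r patients be resampled and s successes remain among the 155−r donors. The expected rate is (s + r·s/(155−r))/155 = s/(155−r), which is the donor success rate.

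**Two scenarios.** All counts are assumptions.

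- (i) 137 counted successes, 4 counted failures, 8 in box 11, 1 each in boxes 9, 10 and 13, 3 lost. Primary 145/155 = 93.5%, SE 2.0.
- (ii) 130 counted successes, 4 counted failures, 12 in box 11, 2, 1 and 2 in boxes 9, 10 and 13, 4 lost. Primary 142/155 = 91.6%, SE 2.2.

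| Rule | (i) | (ii) |
|---|---|---|
| Flags (boxes 4, 11, 12) | 137/144 = 95.1% | 130/139 = 93.5% |
| 7.6.1, box 13 only, box 11 kept | 145/151 = 96.0%; gap 0.9 (about 0.45 SE) | 142/149 = 95.3%; gap 1.8 (about 0.8 SE) |
| 7.6.1, boxes 9, 10 and 13, box 11 kept | 145/149 = 97.3%; gap 2.2 (1.1 SE) | 142/146 = 97.3%; gap 3.7 (1.7 SE) |
| Box 13 redrawn, box 11 redrawn too | 137/143 = 95.8%; gap 0.7 (about 0.3 SE) | 130/137 = 94.9%; gap 1.4 (about 0.6 SE) |

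**When the gap passes one SE.** Fix 2 patients in boxes 4 and 12 and 4 in box 11 (assumed), and let F be the number of unflagged failures that are redrawn.

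- At 146/155 the flags give 142/149 = 95.30%. The text gives 146/(153−F): 95.42% at F=0, 96.05% at F=1 (0.40 SE) and 97.33% at F=3 (1.08 SE).
- At 138/155 the flags give 134/149 = 89.93%. The text gives 138/(153−F): 92.00% at F=3 (0.82 SE), 92.62% at F=4 (1.07 SE) and 93.24% at F=5 (1.32 SE).

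With 0 to 4 patients in boxes 4 and 12 and 0 to 12 in box 11, the threshold is F = 3 to 4 at 94% and 3 to 5 at 89%. With F of 0 or 1 the gap stays below about 0.6 SE. Box 11 alone would need 45 patients (94%) or 32 (89%). A simulation of 100 hot-deck draws with F=4 gave 95.28% against 97.99%, and 89.86% against 92.55%, in line with the formula.

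**Are the flags reliable elsewhere?** In SAP 10.3 (month 6), [b] is on box 5 in both columns and on stage 2 box 8. Box 5 is an observed count of 20 or less without signs of relapse. Together these are all the month-6 success boxes. Resampling every flagged patient leaves only failures as donors, and the month-6 fair-case rate becomes 0%. SAP 8.6.2 does apply these sensitivity analyses at month 6.

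**The case against.** **The text defers to Section 10, so the flags govern.** This is a natural default, but the SAP does not say so. The references are circular, since 7.6.1 points to Section 10 and the note there points back to 7.6.1. The month-6 flags also show that the flags cannot be applied unexamined.

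**Box 11 is a probable cure, not a proven one.** This has force. SAP 6.1 distinguishes cure from probable cure, and Protocol 2.2.1 calls a patient who refuses the last puncture after an earlier favourable count a probable cure. The stage 2 month-12 algorithm likewise flags a success carried from month 6 and leaves a success from a later count unflagged. Box 11 is therefore an ambiguity, not a clear contradiction. The disagreement on box 13 remains.

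**Boxes 9 and 10 would not be redrawn in practice.** This also largely stands. They rest on observed evidence, and the rule sits under missing-data handling. Taken with full literalness, the third group would reach even deaths and rescue cases without a month-18 count, which can hardly be intended. The wording still does not exclude any of them.

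**The assumed counts are high.** The documents' only guide is one historical NECT study in SAP 8.6.1.3, with 4 of 143 patients lacking a month-18 assessment, or 155 × 4/143 ≈ 4 here. The scenarios place 11 and 17 patients in boxes 9, 10, 11 and 13.

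**Conclusion.** The mismatch is in the text and needs no assumption: box 13 meets the rule in 7.6.1 and is not flagged in 10.1, boxes 9 and 10 are not excluded by the wording, box 11 is unsettled, and no order of precedence is given.

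The size is conditional. A reader might infer that sensitivity analysis #4 has two answers more than one standard error apart. The documents do not support that as a general statement, because they give no counts for the disputed boxes. With the assumed counts the gap is about 1 to 2 points, under one SE, if only box 13 is redrawn. It exceeds one SE in those scenarios only when boxes 9 and 10 are redrawn as well. What matters is the total of redrawn failures, about 3 of 155 at 94% success to 5 at 89%; box 13 alone would have to hold that many to have the same effect.

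Nor should a reader infer that the primary result is in doubt. The primary analysis does not use the fair case, this is one of six sensitivity analyses, and the study has no formal success rule. The point is a should-fix clarification.

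**What to change.** Use one rule in both places.

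1. In SAP 7.6.1, list the SAP 10.1 box numbers to be resampled at month 18: boxes 4, 12 and 13. State that boxes 1 to 3 and 5 to 10 are never resampled, because their outcomes are observed. Make the [b] flags identical to this list in both columns.
2. Settle box 11 once. Either drop its [b] in both columns, or keep [b] and delete the words *prior or* from the third group in 7.6.1.
3. Apply the same choice to a stage 2 patient with a month-12 count of 20 or less but no month-6 count. That patient fails box 11 and falls to box 13. If box 11 is not resampled, this patient should be kept as a success in the fair case and not redrawn with box 13; if it is resampled, the patient is redrawn either way.
4. Define donors as the patients who are not resampled.
5. In the same edit, correct the [b] flags on month-6 successes in SAP 10.3 (box 5 in both columns, and stage 2 box 8).

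The cost is a few lines of wording and some flag changes before programming. No new data are needed, and Protocol Section 9 provides for SAP amendment before final database lock.

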### **9.1. Sample Size Determination**

The sample size is based on the largest number of patients who can be enrolled within a reasonable timeframe. It is expected that 155 late-stage patients should be enrolled within approximately 2 years. A provision of 5% (7 patients) is planned in order to allow for replacement of patients lost to follow-up who fled the region due to armed conflict or natural disaster. Approximately 50 early- and intermediate-stage patients could be enrolled within this timeframe. As a reminder, enrolment of early- and intermediate-stage patients will begin approximately 6 months after the start of enrolment of late-stage patients and will end at the same time.

If the observed success rate is around 89% (the same as the expected rate for fexinidazole and the observed rate with eflornithine) then the width of the 95% Jeffreys confidence interval will be 9.8% (83.4%–93.2%) for an 89% success rate. The width decreases with an increase in the success rate to reach 7.4% (89.7%–97.1%) for a 94% success rate. In contrast, the precision is not highly sensitive to the sample size. With 200 patients, the width of the confidence interval is 8.7% (84.1%–92.8%) for an 89% success rate. Indeed, the sample size must increase by 50%, i.e. 300 patients instead of 200, to reduce the width of the lower arm of the 95% confidence interval by one percentage point.

In early- and intermediate-stage patients, the expected success rate is around 91%, i.e. the same as for pentamidine. The width of the confidence interval with 50 patients will be of the order of 17%.

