**Sensitivity analysis #4**

The analysis described above (cf. primary analysis) will be performed on Stage 2 patients included in the mITT with the “fair case” method (see [Section 7.6.1](#)).

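### The fair-case sensitivity analysis names a Jeffreys interval, but pooling as specified gives a symmetric t-interval whose lower bound is about 0.7–1 point too high in stage 2 and about 2.4–3 points too high in cohort 2

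*SAP*

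**What the plan says.** SAP Section 7.6.1 (fair case method) fills in missing responses by random draws, with replacement, from the observed responses, and does so 100 times. Each completed sample yields a success rate, a Jeffreys interval and a standard error whose formula is not given. Only the rates and standard errors then go into Rubin's rules in MIANALYZE, "to provide combined estimate and the 95% Jeffrey CI". No transformation is named, and the per-sample Jeffreys limits take no part in the pooling.

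The method serves sensitivity analysis #4 of the primary endpoint, on stage 2 patients "included in the mITT with the “fair case” method". Section 8.6.2 extends the sensitivity analyses to the 6- and 12-month rates in stage 2 and to the 6-, 12- and 18-month rates in stage 1 and intermediate patients (cohort 2). Section 9.1.3 repeats the outputs for stage 1 and intermediate patients separately.

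Section 7.2 fixes the error level: alpha "is set to 0.05, two sided". Section 8.6.1.1 (and Protocol 9.6.1) justifies Jeffreys by its near-equal tails, which matter because the lower limit carries more clinical meaning than the upper.

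**The concern.** The stated rule cannot deliver the stated interval. A programmer must either print a t-interval under a Jeffreys heading or choose another method once the data are in hand. A t-interval for a high proportion is symmetric where the Jeffreys interval is skewed downwards, so its lower limit errs in the drug's favour.

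The study has no formal success rule (Protocol 9.6.2, SAP 8.7). The result is read from the observed rate and the lower limit, set against historical NECT figures. The fair-case table would also sit beside tables with true Jeffreys intervals, so a reader could take a change of interval method for an effect of missing data.

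**Working it through.** **Inputs.** Protocol 9.1 gives the sizes and rates. For stage 2: "It is expected that 155 late-stage patients should be enrolled within approximately 2 years", with planning rates of 89% and, as a higher scenario, 94%. For cohort 2, "the expected success rate is around 91%, i.e. the same as for pentamidine", with 50 patients. The documents do not say how many outcomes will be re-sampled. I assume 5 of 155 and 3 of 50.

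**1. The plan's own figures.** Jeffreys limits are the 2.5th and 97.5th percentiles of Beta(x+0.5, n−x+0.5).
- 138/155 gives 83.4–93.2, width 9.8. The plan says "95% Jeffreys confidence interval will be 9.8% (83.4%–93.2%) for an 89% success rate".
- 146/155 gives 89.7–97.1, width 7.4. The plan says "to reach 7.4% (89.7%–97.1%) for a 94% success rate".
- 45/50 gives 79.5–96.1, width 16.6. The plan says "The width of the confidence interval with 50 patients will be of the order of 17" per cent.

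All three reproduce.

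**2. What the pooling produces.** Let p_i be the rate and U_i the squared SE in sample i, and let M = 100. Then Q = mean(p_i), B = variance of the p_i, T = mean(U_i) + (1 + 1/M)B, and the limits are Q ± t × sqrt(T). I take U = p(1−p)/n as the usual SE.

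**3. No missing data.**
- 138/155: SE = sqrt(0.8903 × 0.1097/155) = 2.51 points, so 84.11–93.95, against Jeffreys 83.40–93.23. The lower limit is 0.71 higher.
- 146/155: 90.51–97.88, against 89.67–97.09. The lower limit is 0.84 higher.

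**4. With imputation.** Take 133/150 observed and 5 imputed, using expected values over the hot-deck draws. Here p = 0.8867 and p(1−p) = 0.1005.
- B = 5 × 0.1005/155² = 0.0000209
- mean U = 0.000648
- T = 0.000648 + 1.01 × 0.0000209 = 0.000669, so sqrt(T) = 2.587 points
- The degrees of freedom are about 99,000, so t = 1.96.
- Limits: 88.67 ± 5.07 = 83.6–93.7

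The comparator pools Beta(x+0.5, n−x+0.5) over the imputed data sets.

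| Observed + imputed | Rubin t-interval | Pooled Jeffreys | Lower limit too high by |
|---|---|---|---|
| 133/150 + 5 | 83.6–93.7 | 82.9–93.0 | 0.7 |
| 141/150 + 5 | 90.2–97.8 | 89.4–97.0 | 0.8 |
| 145/150 + 5 | 93.8–99.5 | 92.9–98.7 | 0.9 |
| 147/150 + 5 | 95.8–100.2 | 94.8–99.4 | 1.0 |
| 43/47 + 3 | 83.5–99.4 | 81.1–97.1 | 2.4 |
| 46/47 + 3 | 93.8–102.0 | 90.7–99.8 | 3.1 |

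Rows 1, 2 and 5 are close to the planning rates of 89%, 94% and 91%. A single run of 100 draws moves the lower limit by a standard deviation of up to about 0.06 point in stage 2 and 0.2 point in cohort 2.

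**5. Tail error with complete data, n = 155.** The chance that the lower limit lies above the true rate should be 2.5%. At a true 94% it is 4.1% for the Wald interval and 1.5% for Jeffreys. At 97.6%, a NECT mITT rate in SAP Table 4, it is 11% and 2.3%.

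**6. When the upper limit passes 100%.** Without missing data this needs p > n/(n + 1.96²).
- n = 155: 155/158.84 = 97.6%. The first count is 152/155, upper limit 100.2.
- n = 50: 50/53.84 = 92.9%. The first count is 47/50, upper limit 100.6.

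If the true cohort 2 rate is 91%, the binomial probability of 47 or more successes in 50 is about 0.33.

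**7. No observed failure.** Every donor is then a success, so every p_i = 1 and B = 0. With U = p(1−p)/n, T = 0 and the interval is 100–100. The Jeffreys interval is 98.4–100 (155/155) or 95.1–100 (50/50). If the SE is instead the Jeffreys posterior standard deviation, the pooled interval is 99.1–100.9 or 97.3–102.7.

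**The case against.** The strongest reply is that little depends on this. It is one of six sensitivity analyses, the primary estimate and its Jeffreys interval are untouched, and no threshold is tested. Sensitivity analysis #6 (observed case) already gives a direct Jeffreys interval. With 133/150 that is 82.9–93.0, the same to one decimal as the pooled Jeffreys interval, although the two analyses do not treat exactly the same patients as missing. All of this stands and limits the weight of the point. It does not make the stated rule workable, and it does not correct the label.

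Two stronger readings are tempting and are not supported.
- A reader might infer that the interval runs above 100% at the expected success rates. It does not: at about 89% and 94% of 155 and about 91% of 50, the upper limits are 93.7, 97.8 and 99.4. The exception would be the separate stage 1 and intermediate tables. At 91%, the limit passes 100% when n is below 0.91 × 1.96²/0.09, about 39. The documents do not give the split between these two groups.
- A reader might infer that a collapse to zero width is built in. It needs the usual SE, which the SAP does not specify, and no failure at all among observed outcomes, where any death, rescue treatment or detected trypanosome counts as a failure. SAS was not run, and MIANALYZE might return missing limits in that case.

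**Conclusion.** The point holds as a mismatch between method and label with a modest, one-directional effect. Rubin pooling of a proportion and its SE gives a symmetric t-interval, so the Jeffreys interval the SAP promises will not come out. The lower limit is about 0.7–1 point too high in stage 2 and about 2.4–3 points too high in cohort 2. Upper limits above 100% arise from about 98% success in 155 patients or 94% in 50, which is plausible in cohort 2. With no failure observed, neither natural choice of SE gives a usable interval.

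The sizes rest on 5 of 155 and 3 of 50 imputed (assumed) and on SE = sqrt(p(1−p)/n). The mislabelling rests on neither. The stage 2 gap is already 0.7–0.8 point with nothing imputed. The change is worth making because it is cheap and concerns the limit on which the plan places most weight, but it does not bear on the primary analysis.

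**What to change.** Replace the last pooling step in SAP Section 7.6.1. For each of the 100 imputed data sets, with x successes among n patients, draw a fixed, stated number of values from Beta(x+0.5, n−x+0.5). Pool all draws and report their mean with the 2.5th and 97.5th percentiles. This carries the Jeffreys interval over to multiple imputation, stays within 0–100%, and matches the intervals in the neighbouring tables.

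If Rubin's rules are kept, state the SE formula, pool on a scale that respects 0–100% (such as the logit) and back-transform, say what is done when no failure is observed, and stop calling the interval Jeffreys.

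An approximate Bayesian bootstrap step before donor selection is optional. It moved no limit by more than 0.1 point in the scenarios tried.

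Cost: a few lines of code, a short SAP edit, and a slightly less favourable lower limit in a sensitivity analysis.
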